
 To describe the safety profile of NasoVAX in healthy adults when administered by intranasal spray at a single dose of 1×10^9, 1×10^{10}, or 1×10^{11} viral particles (vp) 	
 Reactogenicity: counts and percentages of subjects with local events (nasal irritation, sneezing, nasal congestion, cough, sore throat, change in smell, change in taste, change in vision, eye pain) and systemic events (headache, fatigue, muscle ache, nausea, vomiting, diarrhea, chills, fever) for 14 days after vaccination Adverse Events (AEs): counts and percentages of subjects with AEs from Day 1 to Day 29; medically attended adverse events (MAEs), serious adverse events (SAEs), new-onset chronic illness (NCI) from Day 1 to Day 181
Secondary Objective	

 To evaluate the humoral immune response to NasoVAX when administered by intranasal spray at a single dose of 1×10^9, 1×10^{10}, or 1×10^{11} vp 	
 Antibody level measured by hemagglutination inhibition (HAI) in serum: 
 Geometric mean titer (GMT): the antilog of the mean of the log-transformed titers Geometric mean ratio (GMR): the ratio of postvaccination and prevaccination GMTs within the same dose group Seroprotection rate (SPR): the percentage of subjects with a HAI titer $\geq 1:40$ Seroconversion rate (SCR): the percentage of subjects with either a baseline HAI titer $< 1:10$ and a postvaccination titer $\geq 1:40$ (which is 4 times the assay lower limit of quantitation), or a baseline HAI titer $\geq 1:10$ and a 4-fold increase in postvaccination HAI titer relative to baseline Antibody level measured by microneutralization (MN) in serum: 
 GMT Responder rate: the proportion of subjects with 2-fold and 4-fold rise since baseline

OBJECTIVES	ENDPOINTS
Exploratory Objectives	

 To evaluate the cellular immune response to NasoVAX when administered by intranasal spray at a single dose of 1×10^9, 1×10^{10}, or 1×10^{11} vp 	
 Spot-forming units (SFUs) to hemagglutinin (HA) peptides measured by enzyme-linked immunosorbent spot assay (ELISpot) in peripheral blood mononuclear cells (PBMCs): 
 Geometric mean SFUs Responder rate: the number and percentage of subjects with 3-fold rise since baseline and 25 SFU/million cells greater than baseline

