
 To evaluate the mucosal immune response NasoVAX when administered by intranasal spray at a single dose of 1×10^9, 1×10^{10}, or 1×10^{11} vp 	
 Immunoglobulin A (IgA) antibody level measured by enzyme-linked immunosorbent assay (ELISA): 
 GMT GMR

 To evaluate the humoral immune response against nonrepresented influenza strains after NasoVAX administration 	
 Antibody level measured by HAI and MN in serum against each strain tested: 
 GMT GMR Responder rate: the number and percentage of subjects with 2-fold and 4-fold rise since baseline

 To evaluate the effect of predose adenovirus serotype 5 (Ad5) serum antibody levels on the immunogenicity of NasoVAX 	
 Predose Ad5 antibody GMT measured by MN in serum Day 29 GMR and responder rate from antibody level measured by HAI in serum

 To compare immunogenicity results to those obtained from banked samples from a previous study of licensed seasonal vaccine in a similar subject population (ALT-FLZ-401) 	
 Antibody level measured by HAI in serum: 
 GMT GMR SPR SCR Antibody level measured by MN in serum: 
 GMT Responder rate SFUs to hemagglutinin peptides measured by ELISpot in PBMCs: 
 Geometric mean SFUs Responder rate IgA antibody level measured by ELISA: 
 GMT GMR

4 Study Design

Study ALT-103-201 is a Phase 2a, randomized, double-blind, placebo-controlled trial to evaluate the safety, and immunogenicity of NasoVAX in healthy adults 18 to 49 years of age. Subjects will be screened within 28 days of randomization (Day 1). Approximately 60 subjects who meet all inclusion and no exclusion criteria and provide written informed consent will be enrolled into 3 sequential cohorts of 20 subjects each defined by the viral particle dose (1×10^9 , 1×10^{10} , and 1×10^{11} vp). Within each cohort and its sentinel group, subjects will be randomized in a 3:1 ratio to receive 1 intranasal dose of NasoVAX or placebo (Day 1) as shown in Table 4-1.

Table 4-1 NasoVax Study Design

Cohort	Dose (vp)	Number of Subjects	
		NasoVAX	Placebo
1	1×10^9	15	5
2	1×10^{10}	15	5

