obtained from the model via ESTIMATE statements. Back-transforming the difference of LS mean estimates and their 95% CIs to the original scale results in a ratio of the geometric means—these ratios will be reported in the summary.

Categorical data derived from the assay data (e.g., SPR, SCR, and responder rate) will be tabulated by counts and percentages per dose group, as well as the 95% Clopper-Pearson exact CI of the percentage. 95% CIs will also be presented to compare the response rate of each NasoVAX dose group to placebo and Fluzone (if applicable). CIs will be calculated in SAS PROC FREQ using the EXACT binomial-option for the individual dose groups and by the METHOD=SCORE riskdiff-option for the differences in dose groups [2]. In addition, comparisons of responders in each NasoVAX dose group against the placebo group and against the Fluzone group (if applicable) will be conducted using Fisher's exact test.

In addition, scatterplots of baseline Ad5 antibody levels along the x-axis will be presented with each of the following variables along the y-axis: HAI antibody titer at Day 29, ELISpot response at Day 8, and IgA response at Day 29 (one plot per dependent variable).

All data related to immunogenicity collection and analysis will be listed.

The logo for Summit Analytical features a stylized mountain range in the background, with a yellow sun rising behind the peaks. Below the graphic, the word "SUMMITANALYTICAL" is written in a light gray, sans-serif, all-caps font.

SUMMITANALYTICAL

9 References

1. Food and Drug Administration. Guidance for industry: Toxicity grading scale for healthy adult and adolescent volunteers enrolled in preventive vaccine clinical trials. Rockville, MD: U.S. Department of Health and Human Services; 2007b. Available at:
<http://www.fda.gov/downloads/BiologicsBloodVaccines/GuidanceComplianceRegulatoryInformation/Guidances/Vaccines/ucm091977.pdf>.
2. Newcombe RG. Interval estimation for the difference between independent proportions: comparison of eleven methods. *Statistics in Medicine* 1998 Apr 30;17(8):873-90

The logo for Summit Analytical features a stylized mountain range with a sun rising behind it. The sun is depicted as a yellow circle with rays, and the mountain peaks are represented by a series of curved lines in shades of yellow and grey. Below the graphic, the company name "SUMMIT ANALYTICAL" is written in a bold, sans-serif font, with "SUMMIT" in a darker grey and "ANALYTICAL" in a lighter grey.

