14.4.1.2	Summary and Analysis of A/California 2009 Antibody Level Measured by MN in Serum by Visit	Per-protocol
14.4.1.3	Summary and Analysis of Cellular Response to A/California 2009 Peptides Measured by IFN-ELISpot in PBMCs by Visit	Per-protocol
14.4.1.4	Summary and Analysis of IgA Antibody Level in Nasopharyngeal Swabs Measured by ELISA by Visit	Per-protocol
14.4.1.5	Summary and Analysis of Antibody Level Measured by HAI in Serum Against Nonrepresented Influenza Strains by Strain and Visit	Per-protocol
14.4.1.6	Summary and Analysis of Antibody Level Measured by MN in Serum Against Nonrepresented Influenza Strains by Strain and Visit	Per-protocol
14.4.1.7	Summary and Analysis of Ad5 Antibody Levels in Serum by Visit	Per-protocol

Figure No.	Description of Figure	Population
14.4.1.1	Geometric Mean (95% CI) of A/California 2009 Antibody Level Measured by HAI in Serum by Dose Group	Per-protocol
14.4.1.2	Geometric Mean (95% CI) of A/California 2009 Antibody Level Measured by MN in Serum by Dose Group	Per-protocol
14.4.1.3	Geometric Mean (95% CI) of Cellular Response to A/California 2009 Peptides Measured by IFN-ELISpot in PBMCs by Dose Group	Per-protocol
14.4.1.4	Geometric Mean (95% CI) IgA Antibody Level in Nasopharyngeal Swabs Measured by ELISA by Dose Group	Per-protocol
14.4.1.5	Geometric Mean (95% CI) of Antibody Level Measured by HAI in Serum Against Nonrepresented Influenza Strains by Strain and Dose Group	Per-protocol
14.4.1.6	Geometric Mean (95% CI) of Antibody Level Measured by MN in Serum Against Nonrepresented Influenza Strains by Antigen and Dose Group	Per-protocol
14.4.1.7	Geometric Mean (95% CI) of Ad5 Antibody Levels in Serum by Dose Group	Per-protocol
14.4.2.1	Scatterplot of Baseline Ad5 Antibody Titer and HAI Antibody Titer at Day 29 by Dose Group	Per-protocol
14.4.2.2	Scatterplot of Baseline Ad5 Antibody Titer and Day 8 ELISpot SFUs by Dose Group	Per-protocol
14.4.2.3	Scatterplot of Baseline Ad5 Antibody Titer and Day 29 IgA Antibody Level by Dose Group	Per-protocol

Listing No.	Description of Listing
16.2.1.1	Subject Disposition
16.2.1.2	Treatment Assignment and Analysis Populations
16.2.1.3	Eligibility, Inclusion and Exclusion Criteria
16.2.2.1	Protocol Deviations
16.2.2.2	Demographics
16.2.2.3	Medical/Surgical History
16.2.3	Vaccination Administration
16.2.4	Prior and Concomitant Medications
16.2.5	Immunogenicity Results
16.2.6	Reactogenicity Events (Subject Diary)

16.2.7	Adverse Events
16.2.8.1	Laboratory Results – Hematology

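### The exploratory Ad5 objective names Day 29 HAI GMR and responder rate, but the SAP relates Ad5 to response only by scatterplots, with HAI as unadjusted Day 29 titre and no effect estimate planned

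*SAP*

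**What the plan says.** SAP Section 3 lists, among the exploratory objectives, "To evaluate the effect of predose adenovirus serotype 5 (Ad5) serum antibody levels on the immunogenicity of NasoVAX". Two endpoints stand beside it: "Predose Ad5 antibody GMT measured by MN in serum" and "Day 29 GMR and responder rate from antibody level measured by HAI in serum". The same section defines GMR as "the ratio of postvaccination and prevaccination GMTs within the same dose group", so it is a group-level quantity. No subject-level fold rise is defined for the Ad5 question.

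Section 8.6 then says that "scatterplots of baseline Ad5 antibody levels along the x-axis will be presented", with these variables on the y-axis: "HAI antibody titer at Day 29, ELISpot response at Day 8, and IgA response at Day 29". Section 10.1 lists them as Figures 14.4.2.1 to 14.4.2.3, each by dose group. The first is titled "Scatterplot of Baseline Ad5 Antibody Titer and HAI Antibody Titer at Day 29 by Dose Group".

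The other relevant outputs do not connect Ad5 to HAI. Table 14.4.1.7 summarises Ad5 antibody by visit. Table 14.4.1.1 summarises A/California HAI by visit and dose group. The ANCOVA in Section 8.6 has dose group and the assay's own log baseline as its only terms.

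**The concern.** An objective about the effect of pre-existing vector antibody needs some quantity that measures that effect. Both named response endpoints are relative to baseline: GMR is a post/pre ratio, and responder rate is defined elsewhere in Section 3 by rise since baseline. The planned HAI display uses absolute Day 29 titre, without the baseline adjustment that the SAP applies in its own ANCOVA.

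Absolute Day 29 titre is the sum, on the log scale, of what the subject brought to the trial and what the vaccine added. If baseline influenza titre varies, it adds scatter that has nothing to do with Ad5 and the vaccine. If it happens to correlate with Ad5 titre (for example through age or exposure history), it produces a pattern when Ad5 has no effect on the response. For an Ad5-vectored vaccine, this is the display on which a reader would judge whether vector immunity matters.

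**Working it through.** **Setting the endpoint against the outputs**

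| Element of the Ad5 objective (Section 3) | Planned output | Related to Ad5 level? |
|---|---|---|
| Predose Ad5 GMT | Table 8-1; Table 14.4.1.7 | It is the Ad5 summary itself |
| Day 29 HAI GMR | Table 8-1; Table 14.4.1.1, by dose group | No |
| HAI responder rate | Table 8-1 marks SPR and SCR for A/California HAI, not Responder Rate; that column is marked for HAI only against nonrepresented strains | No |
| Effect of Ad5 on response | Three scatterplots; no slope, correlation, stratum or interval | Visually only |

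Section 7.4.1 reports one change from the protocols, to the PP definition, and does not mention the Ad5 endpoint.

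**Size of the mixing problem**

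The documents state no figure for the Ad5 analysis. The number of NasoVAX recipients, 45 (15 per dose), comes from Sections 4 and 7.1. Two-sided 0.05 comes from Section 7.4. As a check on that n, the adverse-event statement in Section 7.1 reproduces: 1 - 0.964^45 = 80.8%, against 80% stated.

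Everything else is assumed: correlation r = -0.40 between log Ad5 and log2 HAI rise, rise SD (sR) 1.5 log2, baseline SD (sB) 1 to 2 log2, and correlation c between baseline and rise of 0 or -0.4.

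Write log2 Day 29 titre as baseline B plus rise R. With Ad5 uncorrelated with B:

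corr(Ad5, Day 29) = r × sR / sqrt(sB² + sR² + 2c·sB·sR)

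Example with sB = 1: for c = 0, -0.40 × 1.5 / sqrt(1 + 2.25) = -0.333; for c = -0.4, -0.40 × 1.5 / sqrt(1 + 2.25 - 1.2) = -0.419.

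Power uses Fisher's z, approximately Φ(|atanh r| × sqrt(n - 3) - 1.96). For fold rise, atanh(0.40) × sqrt(42) = 2.745, giving 78%.

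| sB (log2) | Raw titre, c = 0: r; power | Raw titre, c = -0.4: r; power | Fold rise: power |
|---|---|---|---|
| 1.0 | -0.333; 61% | -0.419; 82% | 78% |
| 1.5 | -0.283; 47% | -0.365; 70% | 78% |
| 2.0 | -0.240; 35% | -0.306; 53% | 78% |

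Raw titre loses nothing once 2c·sB·sR = -sB², that is c = -sB/(2·sR): -0.33, -0.50 and -0.67 for sB of 1, 1.5 and 2.

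Within one dose group (n = 15), fold rise has 31% power, against 22% to 14% on raw titre when c = 0.

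**Error in the other direction**

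Suppose Ad5 has no effect on the rise but correlates 0.3 with baseline HAI, and baseline is independent of rise. Then corr(Ad5, Day 29) = 0.3 × sB / sqrt(sB² + sR²). This runs from 0.3 × 0.75/1.677 = 0.13 (sB = 0.75) to 0.3 × 2/2.5 = 0.24 (sB = 2). A 5% test would be significant in 14% to 35% of trials.

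**Simulation check**

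4,000 runs, n = 45, two-fold HAI steps, values below 10 set to 5 as in Section 7.4.8, baseline independent of rise:

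- r = -0.40 and sB = 1.5: power 45% on raw titre, 73% on fold rise, 72% on baseline-adjusted Day 29 titre.
- No Ad5 effect, Ad5-baseline correlation 0.3, sB 1.5 to 2: false-positive rate 28% to 35% on raw titre, 5% to 6% on fold rise or adjusted titre.

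**The case against.** Several points on the other side stand.

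- The objective is exploratory. Section 7.1 says the trial was not sized for power, and no Ad5 test is planned. The power figures therefore measure how much signal each y-axis carries; they do not describe a planned test.
- A reader might infer that the plan never produces the endpoint. The documents do not support that. Predose Ad5 GMT, Day 29 HAI GMR and SCR are all tabulated. What is missing is the link between them and Ad5 level, plus an HAI responder rate under that name for A/California.
- A reader might also infer that all the Ad5 plots use raw Day 29 titre. Only one does; the others use Day 8 ELISpot and Day 29 IgA.
- GMR as defined has no subject-level value, so it could not simply be placed on a scatterplot.
- The dilution depends on baseline being independent of rise. With a moderate negative correlation, raw titre can match or beat fold rise.
- The figures are by dose group. At 15 per dose, no choice of y-axis is very informative.
- The table and figure shells (Section 10.2) and the ALT-103-201 protocol are not among the documents. A fitted line or a limit on baseline titre cannot be excluded.
- All immunogenicity data are listed, and Section 7.4 allows labelled post-hoc analyses.

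These points limit the severity without closing the gap. A post-hoc analysis does not stand in for a prespecified endpoint, and nothing in the SAP explains the change from baseline-relative endpoints to an absolute titre.

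**Conclusion.** The mismatch between Sections 3 and 8.6 is established from the text alone. The Ad5 objective names two baseline-relative HAI endpoints, the plan relates Ad5 to neither, and no effect estimate is planned.

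The statistical consequence is conditional. Unadjusted Day 29 titre can weaken a true association (78% power falling to between 61% and 35% under independence), make little difference or slightly help (82% or 70% with baseline and rise correlating -0.4 and baseline SD 1 or 1.5), or suggest a false one. A reader might infer that the planned plot is insensitive and that a real Ad5 effect would be missed. The documents do not support this, because they give no SDs, no Ad5-rise correlation and no baseline-rise correlation. What can be said is that the plot cannot separate pre-existing influenza antibody from vaccine response, whereas a baseline-adjusted model can.

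Severity is low, because the objective is exploratory and the study is not powered.

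**What to change.** In Section 8.6, for NasoVAX recipients pooled over dose, prespecify a linear model of log Day 29 HAI on dose group, log baseline HAI and log baseline Ad5. Report the Ad5 slope as the fold-change in Day 29 GMT per 2-fold higher Ad5, with 95% CI, labelled exploratory. With log baseline HAI in the model, this slope is the same whether the outcome is log Day 29 titre or log fold rise, so it also answers the GMR endpoint. It is safer than fold rise alone, which can itself depend on baseline.

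Define the subject-level Day 29/Day 1 fold rise in the SAP and use it as the y-axis of Figure 14.4.2.1. Show HAI seroconversion by baseline Ad5, and state whether seroconversion is what Section 3 means by HAI responder rate. Extending the approach to ELISpot and IgA is optional, since Section 3 ties this objective to HAI only.

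The cost is SAP wording, one extra model, one redrawn figure and one small display. Day 1 and Day 29 HAI and Day 1 Ad5 are already scheduled. The additions should be filed before the Day 29 interim unblinding in Section 7.3; after that they would be post hoc. The pooled model assumes a common Ad5 slope across doses, and intervals will be wide: an observed correlation of -0.40 at n = 45 has a 95% CI of tanh(-0.424 ± 1.96/sqrt(42)), about -0.62 to -0.12.

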10.1 List of Tables, Figures, and Listings

Table No.	Description of Table	Population
14.1.1	Subject Disposition	All Subjects
14.1.2.1	Demographics and Baseline Characteristics	Safety
14.1.2.2	Demographics and Baseline Characteristics	ITT
14.1.2.3	Demographics and Baseline Characteristics	Per-protocol
14.1.3	Medical/Surgical History	Safety
14.2.1	Concomitant Medications	Safety
14.2.2	Concomitant Medications Started Prior to Study Treatment	Safety
14.3.1.1	Summary and Analysis of Worst Reactogenicity Events by Grade	Safety
14.3.1.2	Summary of Worst Reactogenicity Events by Event Type and Grade	Safety
14.3.1.3	Summary of Duration of Reactogenicity Events by Event Type	Safety
14.3.2.1	Overall Summary of Adverse Events	Safety
14.3.2.2	Treatment Emergent Adverse Events (TEAE) by System Organ Class and Preferred Term	Safety
14.3.2.3	Treatment Emergent Adverse Events (TEAE) by System Organ Class and Severity	Safety
14.3.2.4	Treatment Emergent Adverse Events (TEAE) by Preferred Term and Relationship to Study Treatment	Safety
14.3.2.5	Serious Treatment Emergent Adverse Events (TEAE) by System Organ Class and Preferred Term	Safety
14.3.2.6	Treatment Emergent Adverse Events (TEAE) Resulting in Dose Withdrawal by System Organ Class and Preferred Term	Safety
14.3.2.7	Treatment Emergent Medically Attended Adverse Events (MAE) by System Organ Class and Preferred Term	Safety
14.3.2.8	Treatment Emergent New-onset Chronic Illnesses (NCI) by System Organ Class and Preferred Term	Safety
14.3.2.9	Listing of Serious Treatment Emergent Adverse Events	Safety
14.3.3.1	Change from Baseline in Hematology Parameters by Visit	Safety
14.3.3.2	Change from Baseline in Chemistry Parameters by Visit	Safety
14.3.3.3	Shift from Baseline in Hematology Parameters Utilizing Toxicity Grade by Visit	Safety
14.3.3.4	Shift from Baseline in Serum Chemistry Parameters Utilizing Toxicity Grade by Visit	Safety
14.3.3.5	Shift from Baseline in Urinalysis Parameters Utilizing Toxicity Grade by Visit	Safety
14.3.4	Change from Baseline in Vital Sign Parameters by Visit	Safety
14.3.5	Summary of Ad5 Vector Shedding by qPCR of Nasopharyngeal Swabs (copies/5µl) by Visit	Safety
14.3.6.1	Change from Baseline in ECG Parameters by Visit	Safety
14.3.6.2	Shift from Baseline in ECG Overall Interpretation at Day 29	Safety
14.4.1.1	Summary and Analysis of A/California 2009 Antibody Level Measured by HAI in Serum by Visit	Per-protocol

14.4.1.2	Summary and Analysis of A/California 2009 Antibody Level Measured by MN in Serum by Visit	Per-protocol
14.4.1.3	Summary and Analysis of Cellular Response to A/California 2009 Peptides Measured by IFN-ELISpot in PBMCs by Visit	Per-protocol
14.4.1.4	Summary and Analysis of IgA Antibody Level in Nasopharyngeal Swabs Measured by ELISA by Visit	Per-protocol
14.4.1.5	Summary and Analysis of Antibody Level Measured by HAI in Serum Against Nonrepresented Influenza Strains by Strain and Visit	Per-protocol
14.4.1.6	Summary and Analysis of Antibody Level Measured by MN in Serum Against Nonrepresented Influenza Strains by Strain and Visit	Per-protocol
14.4.1.7	Summary and Analysis of Ad5 Antibody Levels in Serum by Visit	Per-protocol

Figure No.	Description of Figure	Population
14.4.1.1	Geometric Mean (95% CI) of A/California 2009 Antibody Level Measured by HAI in Serum by Dose Group	Per-protocol
14.4.1.2	Geometric Mean (95% CI) of A/California 2009 Antibody Level Measured by MN in Serum by Dose Group	Per-protocol
14.4.1.3	Geometric Mean (95% CI) of Cellular Response to A/California 2009 Peptides Measured by IFN-ELISpot in PBMCs by Dose Group	Per-protocol
14.4.1.4	Geometric Mean (95% CI) IgA Antibody Level in Nasopharyngeal Swabs Measured by ELISA by Dose Group	Per-protocol
14.4.1.5	Geometric Mean (95% CI) of Antibody Level Measured by HAI in Serum Against Nonrepresented Influenza Strains by Strain and Dose Group	Per-protocol
14.4.1.6	Geometric Mean (95% CI) of Antibody Level Measured by MN in Serum Against Nonrepresented Influenza Strains by Antigen and Dose Group	Per-protocol
14.4.1.7	Geometric Mean (95% CI) of Ad5 Antibody Levels in Serum by Dose Group	Per-protocol
14.4.2.1	Scatterplot of Baseline Ad5 Antibody Titer and HAI Antibody Titer at Day 29 by Dose Group	Per-protocol
14.4.2.2	Scatterplot of Baseline Ad5 Antibody Titer and Day 8 ELISpot SFUs by Dose Group	Per-protocol
14.4.2.3	Scatterplot of Baseline Ad5 Antibody Titer and Day 29 IgA Antibody Level by Dose Group	Per-protocol

Listing No.	Description of Listing
16.2.1.1	Subject Disposition
16.2.1.2	Treatment Assignment and Analysis Populations
16.2.1.3	Eligibility, Inclusion and Exclusion Criteria
16.2.2.1	Protocol Deviations
16.2.2.2	Demographics
16.2.2.3	Medical/Surgical History
16.2.3	Vaccination Administration
16.2.4	Prior and Concomitant Medications
16.2.5	Immunogenicity Results
16.2.6	Reactogenicity Events (Subject Diary)

16.2.7	Adverse Events
16.2.8.1	Laboratory Results – Hematology
16.2.8.2	Laboratory Results – Serum Chemistry
16.2.8.3	Laboratory Results – Urinalysis
16.2.8.4	Drug and Alcohol Screen
16.2.8.5	Pregnancy Test
16.2.8.6	Serology Tests
16.2.9	Ad5 Vector Shedding by qPCR Assay
16.2.10	Viral Culture
16.2.11	ECG Parameters
16.2.12	Vital Signs
16.2.13	Physical Examination

10.2 Mock Tables, Figures, and Listings

Please refer to the separate document of table, figure, and listing shells and programming notes.

SUMMIT ANALYTICAL
